8.3.2 Exclusion Criteria

Subjects who meet any of the following criteria will be excluded from the study:

1. Wrinkle Severity Rating Scale Score of ≤ 2 on the right or left nasolabial fold.
2. Women who are pregnant or lactating.
3. Received prior dermabrasion, facelift, or Botox below the orbital rim within 6 months (180 days) prior to entry into the study.

4. Previous tissue augmentation (bulking agents) for facial wrinkles and scars within 6 months (180 days) at the proposed injection sites.
5. Previous tissue augmentation with permanent implants.
6. Evidence of scar-related disease or delayed healing activity within the past 1 year.
7. Scars at the intended treatment sites.
8. History of keloid formation or hypertrophic scars.
9. Any infection or wound on the face.
10. Allergic history including anaphylaxis or multiple severe allergies to natural rubber latex or lidocaine.
11. Aspirin or nonsteroidal anti-inflammatory drugs within 1 week (7 days) prior to treatment.
12. Concomitant anticoagulant therapy, antiplatelet therapy, or history of bleeding disorders or connective tissue disorders.
13. Over-the-counter (OTC) wrinkle products or prescription wrinkle treatments within 4 weeks (28 days) prior to treatment and throughout the study.
14. Immunocompromised or immunosuppressed.
15. Clinically significant organic disease including clinically significant cardiovascular, hepatic, pulmonary, neurologic, or renal disease or other medical condition, serious intercurrent illness, or extenuating circumstance that, in the opinion of the investigator, preclude participation in the trial.
16. Received any investigational product within 30 days of signing the Informed Consent Form.
17. Facial tattoo that may interfere with diagnosis.
18. Systemic (oral/injectable) corticosteroids or immunosuppressive medications within 30 days prior to treatment and topical steroids on the face within 14 days prior to treatment start and throughout the study.

8.3.3 *Subject Withdrawal Criteria*

A subject may withdraw from the study at any time for any reason.

A subject will be withdrawn from the study if his/her safety or well-being is determined to be at risk. Withdrawal will be made at the discretion of the investigator or at the subject's request.

A subject must withdraw from the study for any of the following reasons:

- The subject or legal representative withdraws consent
- The subject's product code is unblinded
- There is a significant protocol violation

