8.4.2 Method of Treatment Assignment, Randomization, and/or Stratification

Every subject will receive Revanesse Ultra on one side of the face and Restylane on the other side of the face. The side of the face treated with either product will vary from subject to subject based on the randomization assignment made at Visit 1/Day 1.

Subjects who satisfy all of the inclusion and none of the exclusion criteria will be randomized with respect to which side of the face receives which treatment. Randomization will be performed according to a computer-generated randomization scheme. The randomization scheme will be generated and maintained by an independent third party. A sealed copy of the randomization scheme should be retained at each site and should be available to regulatory authorities at the time of site inspection to allow for verification of the treatment identity for each subject.

A unique subject number will be assigned to each subject. Each site will receive a list of randomization code numbers and corresponding study product boxes. Each eligible subject will be assigned a unique randomization code number in ascending order.

No stratification based on age, sex, or other characteristics will be performed.

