8.4.3 Administration of Dose for Each Subject

Subjects are physically masked (blindfolded) just prior to and during all injection procedures to prevent observation of the syringes containing study product.

Injections of the study product are performed by the unblinded injecting investigator. The blinded evaluator is not allowed to retrieve study supplies or to be present during opening of the study supplies or during the injections. The injecting investigator is not to have any discussion with the blinded evaluator or subjects regarding the treatments.

Up to a maximum of 2.0 mL (2 pre-filled syringes) will be used per treatment on each nasolabial fold similar to the comparator agent based on previous studies and common clinical practice.

The injection will be given intradermally and for best results should be injected in the mid-dermis. The treatment technique and the volume per treatment should be as similar as possible on both sides of the face.

For many patients with moderate NLFs, one syringe will be adequate per NLF. Based on the iGAI score at that time, a touch-up treatment may be administered at Visit 2/Week 1.

For this study, topical anesthetic will not be used. Ice may be applied before the treatment if the injecting investigator deems it necessary. The same technique should be used on both sides of the face. Using the nondominant hand to apply gentle downward traction to the inferiormost aspect of the fold to immobilize it, the dominant hand is used to inject filler. Steadying the injecting hand on the mandible or the other hand, the linear threading technique is most easily used to deposit the filler beneath the fold and efface it.

The peri-alar sulcus, a triangular shaped concavity at the upper end of the fold, may be more effectively filled with the fanning technique of implantation, where two or three threads are deposited in a fan-like array. Wide portions of the fold may require several threads placed side by side, with gentle massage after each thread is placed.

Treatment of this area is generally easy and straightforward. Notice that the fold is partially formed by prominent cheek tissue that is lateral to it, with the fold becoming more prominent as the cheek becomes more protuberant. Therefore, injections should stay medial to the fold to fill it. Injecting lateral to the fold, in the excessive cheek tissue, can actually tend to accentuate the fold.

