8.4.5 Method of Packaging, Labeling, Storage, and Dispensing

Study products will be supplied to the sites in their standard packaging. A label that includes the protocol number and Sponsor name will be attached to each pouch of the Revanesse study product. Restylane study product will be supplied by the sites for their subjects. Investigators will be instructed to follow instructions regarding storage in accordance with the product's Instructions for Use.

All study product will be stored in a climate-controlled, limited access area.

The investigator agrees to store and administer the study product only at the site(s) listed on Form FDA 1572 (or investigator agreement/statement). The investigator, sub-investigator(s), or qualified designees also agree that the study product will be administered only to subjects who have provided written informed consent and have met all entry criteria. Study product may not be used for any purpose other than as stated in the protocol.

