- Revanesse® Ultra is only intended for intradermal use and must not be injected into blood vessels. This may occlude and could cause an embolism.
- Patients who develop hypertrophic scarring should not be treated with Revanesse® Ultra.
- Contains trace amounts of gram positive bacterial proteins, and is contraindicated for patients with a history of allergies to such material.
- Never use Revanesse® Ultra in conjunction with a laser, intense pulsed light, chemical peeling or dermabrasion treatments.
- People under the age of 18 should not be treated with Revanesse® Ultra.
- Patients with acne and / or other inflammatory diseases of the skin should not be treated with Revanesse® Ultra.
- Patients with unattainable expectations.
- Patients with auto-immune disorders or under immunotherapy.
- Patients with multiple severe allergies.
- Patients with acute or chronic skin disease in or near the injection sites.
- Coagulation defects or under anti-coagulation therapy.
- Patients with sensitivity to hyaluronic acid.

It is imperative that patients with adverse inflammatory reactions that persist for more than one week report this immediately to their physician. These conditions should be treated as appropriate (ie: corticosteroids or antibiotics). All other types of adverse reactions should be reported directly to the authorized distributor of the Revanesse® family of products and / or to Prollenium Medical Technologies Inc. directly.

ADMINISTRATION & DOSAGE

- Revanesse® Ultra should only be injected by or under the direct supervision of qualified physicians who have been trained on the proper injection technique for filling facial wrinkles.
- Before patients are treated they should be informed of the indications of the device as well as its contraindications and potential undesirable side effects.
- The area to be treated must be thoroughly disinfected. Be sure to inject only under sterile conditions.
- Revanesse® Ultra and needles packaged with it are for single use only. Do not re-use. If re-used, there is a risk of infection or transmission of blood born diseases.
- Keep the product at room temperature for 30 minutes prior to injection.
- The amount of Revanesse® Ultra that is injected will depend on the severity of the depression or the

level of correction desired.

- If the skin turns a white color (blanching), the injection should be stopped immediately and the area should be massaged until the skin returns to its normal color.

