15.2 Package Insert for Restylane

Restylane®

Printer-Friendly Version*

Caution: Federal Law restricts this device to sale by or on the order of a physician or licensed practitioner.

Description

Restylane is a gel of hyaluronic acid generated by *Streptococcus* species of bacteria, chemically crosslinked with BDE, stabilized and suspended in phosphate buffered saline at pH=7 and concentration of 20 mg/mL.

Indication

Restylane is indicated for mid-to-deep dermal implantation for the correction of moderate to severe facial wrinkles and folds, such as nasolabial folds.

Restylane is indicated for submucosal implantation for lip augmentation in patients over the age of 21.

Contraindications

- Restylane is contraindicated for patients with severe allergies manifested by a history of anaphylaxis or history of presence of multiple severe allergies.
- Restylane contains trace amounts of gram positive bacterial proteins, and is contraindicated for patients with a history of allergies to such material.
- Restylane is contraindicated for patients with bleeding disorders.
- Restylane is contraindicated for implantation in anatomical spaces other than the dermis or submucosal implantation for lip augmentation.

Warnings

- Defer use of Restylane at specific sites in which an active inflammatory process (skin eruptions such as cysts, pimples, rashes, or hives) or infection is present until the process has been controlled.
- Injection site reactions (e.g., swelling, redness, tenderness, or pain) to Restylane have been observed as consisting mainly of short-term minor or moderate inflammatory symptoms starting early after treatment and with less than 7 days duration in the nasolabial folds and less than 14 days duration in the lips. Rare post-market reports of immediate post-injection reactions included extreme swelling of lips, the whole face and symptoms of hypersensitivity such as anaphylactic shock.
- Restylane must not be implanted into blood vessels. Localized superficial necrosis and scarring may occur after injection in or near vessels, such as in the lips, nose, or glabellar area. It is thought to result from the injury, obstruction, or compromise of blood vessels.
- Delayed onset inflammatory papules have been reported following the use of dermal fillers. Inflammatory papules that may occur rarely should be considered and treated as a soft tissue infection.

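### The only allergy exclusion (criterion 10) does not name bacterial-protein allergy, a contraindication on both product labels, and can be read too narrowly

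*Protocol*

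**What the plan says.** Criterion 10 in Protocol section 8.3.2, repeated in the same words in the synopsis (section 3.1), excludes: "Allergic history including anaphylaxis or multiple severe allergies to natural rubber latex or lidocaine". None of the other 17 exclusion criteria and none of the 6 inclusion criteria mentions allergy or hypersensitivity.

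Section 8.4.2 gives both products to everyone: "Every subject will receive Revanesse Ultra on one side of the face and Restylane on the other side of the face". Section 8.4.5 sets the condition for injection: "the study product will be administered only to subjects who have provided written informed consent and have met all entry criteria".

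The labels are appended in section 15. The Restylane insert (15.2) states: "Restylane contains trace amounts of gram positive bacterial proteins, and is contraindicated for patients with a history of allergies to such material". It also states: "Restylane is contraindicated for patients with severe allergies manifested by a history of anaphylaxis or history of presence of multiple severe allergies". The Revanesse Ultra insert (15.1) says of that product: "Contains trace amounts of gram positive bacterial proteins, and is contraindicated for patients with a history of allergies to such material". Its contraindications also include multiple severe allergies, with no allergen named, and sensitivity to hyaluronic acid.

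**The concern.** The eligibility list is what a site applies when it decides whom to inject. If it does not clearly carry the labels' allergy contraindications, a coordinator can clear a patient whom the manufacturers say should not be treated. Because each subject receives both products, a contraindication on either label is enough to make the subject unsuitable.

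The two allergens that criterion 10 does name appear in neither insert's composition statement. Naming them does no harm in itself, but it directs attention to substances the products are not stated to contain while leaving out one that both are stated to contain.

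The matter at stake is subject safety. Exposure can also recur, through the Week 1 touch-up (section 8.6.11) and the open-label Revanesse Ultra injection at Week 24 (section 8.4.3). Section 8.10 counts an increased occurrence of hypersensitivity reactions or anaphylaxis among the causes for terminating the study, so the same risk should be screened for clearly at entry.

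**Working it through.** This is a comparison of texts; no sample size or power figure is involved.

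**Step 1. Label allergy contraindications against criterion 10.**

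| Contraindication | Revanesse Ultra insert (15.1) | Restylane insert (15.2) | Criterion 10 |
|---|---|---|---|
| Allergy to gram-positive bacterial proteins | Yes | Yes | Not named |
| Multiple severe allergies, any allergen | Yes | Yes | Present, but can be read as limited to latex or lidocaine |
| History of anaphylaxis | Not listed separately | Yes | Named |
| Sensitivity to hyaluronic acid | Yes | No | Not named |

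Three contraindications are therefore left unclear: one shared and not named, one shared and ambiguous, one on the Revanesse label only and not named.

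**Step 2. The allergens that are named.** The Revanesse composition statement lists cross-linked hyaluronic acid, phosphate buffered saline and the cross-linking agent. Restylane is described as bacterially generated hyaluronic acid, cross-linked and "stabilized and suspended in phosphate buffered saline". Neither statement mentions lidocaine or latex. Lidocaine does not enter through a topical anesthetic either, since section 8.4.3 says: "For this study, topical anesthetic will not be used".

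**Step 3. Does anything else in the protocol close the gap?**
- Section 6.1 refers to the appended labelling for benefits and risks. It does not make label contraindications into exclusions.
- Section 8.4.5 refers to the Instructions for Use for storage only.
- Criterion 15 lets the investigator exclude for another medical condition or circumstance, but this is discretionary and does not mention allergy.
- Several other label contraindications do have explicit criteria: pregnancy and lactation (2), hypertrophic scars (8), bleeding disorders (12), immune status (14). That makes the allergy gap look like an oversight.

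**Step 4. Likely size.** The documents give no prevalence for any of the three contraindications, so the number of affected patients cannot be calculated. The nearest figures are:
- *Hypersensitivity-type reactions.* The Revanesse insert reports fewer than 1 in 1500 treatments. For 163 first treatments, 163 / 1500 = 0.109, so fewer than 0.11 expected. This is a rate in treated patients generally, not in contraindicated ones.
- *Pre-treatment antibodies to Restylane.* Study MA-1400-02 had 15/142 and study MA-1400-01 had 9/150; together (15 + 9) / (142 + 150) = 24/292 = 8.2%. Antibody positivity is not a history of allergy.
- *Injection-site events.* In MA-1400-02, 7/21 = 33.3% with antibodies against 53/142 = 37.3% overall, with no severe events. In MA-1400-01, 1/6 = 17% against 28/150 = 18.7%. The denominators 21 and 6 do not match the 15 and 9 pre-treatment positives, and the insert does not explain the difference.
- *Hyaluronic acid.* The Restylane insert reports that evaluation of patients with suspected hypersensitivity found no evidence of immune reactions directed at hyaluronic acid itself.

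**The case against.** The strongest reply is that criterion 10 opens with allergic history in general and introduces the rest with the word *including*. Read that way, a known allergy to bacterial protein or hyaluronic acid is already excluded, and nothing restricts multiple severe allergies. That reading is available, but the text does not secure it. If any allergic history excluded a patient, the qualifiers *multiple* and *severe* would have no work to do, so a site can naturally take the narrower meaning.

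A second reply is that meeting the entry criteria is necessary for injection, not an order to inject. A clinician still decides, takes a medical history at Visit 1, has both inserts at hand and can use criterion 15. The side-effects section of the Revanesse insert also says that patients with multiple allergic reactions should not be treated. All this makes injection of a known contraindicated patient less likely. It does not turn label contraindications into exclusions.

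Third, the consent pages were removed and the screening form is not in the documents, so either might already ask about these allergies. That is fair, but the criterion itself would still need to match.

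Fourth, the figures point to little excess harm. That stands, and it limits how much weight the point should carry.

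Finally, replacing the general opening with a closed list might admit someone with one severe, non-anaphylactic allergy to an unlisted substance. This would be a loosening only if the present text excludes every allergic history, and such a patient matches none of the allergy contraindications on either label.

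**Conclusion.** The point holds. Criterion 10 is the only allergy exclusion. It does not name an allergy that both labels contraindicate, it can be read as narrowing a second shared contraindication, and it does not name a third that is on the Revanesse label. No other protocol text makes label contraindications binding at entry.

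The conclusion rests on the wording alone and assumes only that some sites would apply the narrower reading. It concerns subject safety; power and the primary analysis are untouched. About 163 subjects are to be randomized, so at least that many will be screened against this sentence. The number of contraindicated patients among them is unknown, and the practical effect is probably small. The change is worth making because the possible harm falls on the subject and the remedy is simple.

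**What to change.** Reword criterion 10 in section 8.3.2 and in the synopsis, and align the screening form, to read:

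> History of anaphylaxis; multiple severe allergies of any kind; or known allergy to gram-positive bacterial proteins, hyaluronic acid, natural rubber latex or lidocaine.

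This keeps the two allergens already named, frees multiple severe allergies from any particular allergen, and covers every allergy contraindication listed on either label. The cost is one sentence in two places plus the form. There may be some additional screen failures; their number cannot be estimated because the documents give no prevalence.

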A subject may be withdrawn from the study for any of the following reasons:

- Lost to follow-up
- Investigator discretion

Withdrawal is permanent; after a subject has been withdrawn, he/she will not be allowed to enroll again.

If a subject is withdrawn from the study for any reason, the End of Study or Early Termination procedures (Visit 6/Week 24 for subjects who are not retreated at Week 24 or Visit 8/Week 52 for subjects who are retreated at Week 24) should be completed and any outstanding data and study product should be collected. Data, including the date and primary reason for withdrawal, must be documented on the End of Study case report form (CRF) and source document.

If a subject withdraws from the study at any time due to an AE, the reason for withdrawal, the nature of the AE, and its clinical course must be fully documented. The investigator must strive to follow the subject until the AE has resolved, become clinically insignificant, is stabilized, or the subject is lost to follow-up. For any SAE, follow procedures provided in [Section 8.9.5](#)

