8.9.6.2 Unblinding Treatment for a Subject During the Study

Unblinding by the investigator should occur only in the event of an AE or SAE for which it is necessary to know the study treatment to determine an appropriate course of therapy for the subject. In the event of an emergency that requires breaking of the study blind, randomization code envelopes will be maintained by each investigator that can be opened to reveal the study product.

Envelopes that have been opened at the study site must be returned to the sponsor accompanied by a written explanation of the reason why the blind was broken.

If unblinding occurs, the subject must be withdrawn from the study.

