9.1 Analysis Populations

Three populations are defined for the analyses.

- Intent-to-treat (ITT) (safety population): All randomized subjects who received study product.
- Modified intent-to-treat (mITT): All randomized subjects who met the inclusion/exclusion criteria, were randomized, received both study products, and returned for at least 1 post-injection assessment of WSRS score from both sides of the face.
- Per-protocol (PP): All randomized subjects who met all inclusion/exclusion criteria; received both study products; completed Visit 6/Week 24 within the specified window, had data on WSRS score from both sides of the face, and had no significant protocol violations that would affect the treatment evaluation.

Efficacy analyses will be performed on the mITT and PP populations. Safety analyses will be performed on the ITT population.

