9.2 General Considerations

Two-sided hypothesis testing will be conducted for all tests. Resulting p-values less than 0.05 will be considered statistically significant unless noted otherwise. No adjustments of p-values for multiple comparisons will be made. SAS software (version 9.1.3) will be used for all data analyses and tabulations.

Missing efficacy data will be imputed via the last observation carried forward (LOCF) method in the mITT analysis. For the PP population, efficacy analysis will be performed using all the available data without imputation for the missing values.

For demographic and baseline characteristics and the safety profile, each variable will be analyzed using the existing data. Subjects with missing data will be excluded only from the analyses for which data are not available.

9.3 Comparability of Subjects at Baseline (or Demographics, Medical History, Baseline Characteristics, and Concomitant Medications)

Baseline and demographic characteristic variables (including date of birth, sex, race, ethnicity, and Fitzpatrick skin type) will be tabulated using descriptive statistics. For each continuous variable, the summary will include the mean, standard deviation, median, minimum and maximum. For each categorical variable, the summary will include frequencies and percentages.

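### Withdrawal forced by unblinding or a significant protocol violation ends scheduled observation as well as treatment, so surveillance for new events and the blinded Week 24 WSRS are lost and LOCF fills the gap in the supportive mITT analysis

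*Protocol*

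**What the plan says.** Section 8.3.3 opens its mandatory list with "A subject must withdraw from the study for any of the following reasons". Besides withdrawn consent, the list contains "The subject's product code is unblinded" and "There is a significant protocol violation". The same section adds: "Withdrawal is permanent; after a subject has been withdrawn, he/she will not be allowed to enroll again". Section 8.9.6.2 restricts code-breaking: "Unblinding by the investigator should occur only in the event of an AE or SAE", and then only where knowing the treatment is needed to choose therapy. It ends with "If unblinding occurs, the subject must be withdrawn from the study".

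Sections 8.3.3 and 8.9.6.1 ask for end-of-study procedures at withdrawal. Section 8.9.6.1 names only the Visit 6 activities, if possible. Section 8.3.3 names Visit 6, or Visit 8 for retreated subjects.

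On missing data, Section 9.2 says "Missing efficacy data will be imputed via the last observation carried forward (LOCF) method in the mITT analysis", with no imputation in the per-protocol (PP) set. Section 9.1 limits PP to subjects who, among other conditions, "had no significant protocol violations that would affect the treatment evaluation". Section 9.4 makes PP definitive and mITT supportive for the primary endpoint.

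**The concern.** The study products are implants. Both are placed on Day 1 (Section 8.4.3), and touch-up is possible only at Week 1 (Section 8.6.11). Between then and the optional Week 24 retreatment there is no study treatment to stop, so removing a subject in that period only ends the observing.

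Two things are at stake:

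- **Safety.** Subjects unblinded under Section 8.9.6.2 had an adverse event for which product identity mattered. General safety monitoring runs until discharge from the study (Section 8.9.3), so scheduled capture of new or delayed events ends for them. Section 9.6 justifies enrolling 163 subjects, well above the 63 needed for power, by the need for safety data.
- **Efficacy.** A blinded evaluator who is separate from the injector (Sections 8.4.3 and 8.6) could still score Week 24. The rule instead turns an obtainable value into a missing one, which the mITT analysis fills with an earlier score. mITT is the planned companion to an analysis that excludes violators, so this weakens it where it is most needed.

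**Working it through.** **1. The plan's own figure.** Section 9.6 gives a margin of 0.50, an SD of the paired difference of 1.30, a true difference of 0, and 63 PP subjects for 85% power, using the upper bound of a two-sided 95% CI (one-sided 0.025).

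- Normal approximation: n = [1.30 × (1.960 + 1.036) / 0.50]² = 60.7, so 61.
- Noncentral t: the smallest n with at least 85% power is 63 (85.2%).

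The stated figure reproduces.

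**2. Effect on PP power.** The protocol gives no rate of such withdrawals, so the shares are assumed. Noncentral t, SD 1.30:

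| Share of 163 withdrawn | PP subjects left | Power |
|---|---|---|
| 0% | 163 | 99.8% |
| 5% | 154 | 99.7% |
| 10% | 146 | 99.6% |
| 20% | 130 | 99.2% |

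PP falls to 63 only after 163 − 63 = 100 losses (61%).

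**3. Effect on mITT under LOCF.** Let w be the share carried forward. Assume that the true Week 24 difference against the test product equals the margin (0.50), that the difference at the carried-forward visit is 0, and that all 163 subjects are in mITT.

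- Expected observed difference = 0.50 × (1 − w).
- Standard error = 1.30 / √163 = 0.102.
- Chance of declaring non-inferiority ≈ 1 − Φ(1.960 − 0.50w / 0.102).

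| w | Subjects (w × 163) | Expected difference | One-sided error (nominal 2.5%) |
|---|---|---|---|
| 2% | about 3 | 0.490 | 3.1% |
| 5% | about 8 | 0.475 | 4.3% |
| 10% | about 16 | 0.450 | 7.1% |

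Each 5% carried forward moves the expected difference by 0.025 towards non-inferiority. If Week 24 scores were collected after the triggering event, the error would return to 2.5% under the same assumptions.

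**4. Safety passages side by side.**

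- An adverse event that causes withdrawal is to be followed until resolved, insignificant or stable (Sections 8.3.3 and 8.9.3). Serious events are followed until normal or stable (Section 8.9.5), and follow-up may run past the end of the study (Section 8.2).
- No section keeps the scheduled visits for new events after withdrawal, and a violator without an adverse event has no follow-up clause at all.
- The appended inserts describe delayed onset: hypersensitivity-type reactions after 2 to 4 weeks (Revanesse Ultra), and granuloma at 3 weeks to 4 months and mass formation up to 6 months (Restylane).

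**The case against.** Much can be said for the plan, and most of it stands.

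- **Follow-up does not simply stop.** A reader might infer that the subjects with the worst events are abandoned. The documents do not support that. The event behind the withdrawal must still be followed, and Section 8.9.6.2 conditions unblinding on the need to know the product, not on severity. The loss is confined to scheduled visits and capture of new events.
- **The trial's claim is not affected through imputation.** A reader might take the figures above as inflation of the primary error rate. They are not: non-inferiority is judged on PP, which is not imputed, and violations that affect evaluation are outside PP in any case.
- **The illustration is unfavourable by construction.** Section 8.7.3 includes WSRS among the Visit 6 procedures, so a score taken at withdrawal may be a late one. The documents do not give the product difference at earlier visits. With no true product difference at either time there is no bias, and a larger early difference would push the other way. A smaller SD would give larger errors, but the protocol states only 1.30.
- **Few may be affected.** Entry-criteria violators are already outside mITT (Section 9.1), and anyone withdrawn after Visit 6 has a Week 24 score.
- **Observed scores are not always clean.** If the violation is another facial procedure, the Week 24 score may reflect that procedure.

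None of this explains why observation has to end. PP is already protected by Section 9.1, and the evaluator need not learn the code.

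**Conclusion.** The point holds in a limited form. The rule, followed as written, gives up scheduled surveillance and an in-window blinded Week 24 WSRS that could have been obtained, including in subjects unblinded because of an adverse event. The safety part needs no assumption about numbers.

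The statistical part concerns only the supportive mITT result. Its size rests on the assumed share carried forward, zero difference at the carried-forward visit, a true difference at the margin, and all 163 subjects in mITT. At 2% the effect is slight; at 10% the one-sided error is nearly three times nominal (7.1 / 2.5 = 2.8). The documents do not show which share applies. PP power is safe under any plausible number of withdrawals. The point is worth correcting because the correction is cheap, but it does not threaten the primary conclusion.

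**What to change.** Amend Sections 8.3.3 and 8.9.6.2, and reconcile them with the early-termination text in 8.3.3 and 8.9.6.1, to say the following:

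- Unblinding or a significant protocol violation does not end observation. Unless consent is withdrawn, the subject continues the scheduled safety visits and has the Week 24 WSRS scored by an evaluator to whom the code is not disclosed.
- These subjects are flagged. Violations are handled through the PP definition in Section 9.1. That definition does not name unblinding, so state how an unblinded subject counts.
- The mITT analysis uses their observed Week 24 values where they meet its definition.
- pGAI from a subject who knows the code is flagged.

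The change concerns observation only. Rules on eligibility for touch-up or retreatment should be left as they are.

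The cost is amendment wording and a few extra visits. Some observed scores may reflect a prohibited procedure; the flag allows those to be examined in a sensitivity analysis.
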